8.2 Sample Size and Accrual

There is no previous publication for applying 5-ALA to head and neck cancer patients. The sample size calculation is based on the experience of 5-ALA in brain cancer. A literature review study summarized the usage of 5-ALA in patients with malignant Gliomas between 2000 and 2015.3 The sample sizes in the studies included in the review ranged from 11 to 97. The sensitivity ranged from 75% and 95% while the specificity ranged from 53% to 96%. In our study, all tissue samples will be collected from the head and neck cancer patients undergoing standard of care surgical resection. The surgeons will provide the pathologists with the patient resected specimen marked, typically in 4 different regions with 3 regions located within the tumor region and 1 located at the boundary or outer region of the tumor. Each region will be marked according to the associated intensity of the PPIX tissue fluorescence score at that location as no brightness (0), mild brightness (1-pink), moderate brightness (2-orange) or robust brightness (3- lava-like orange). Thus each patient is expected to contribute 1 tissue sample from a normal margin region and 3 tissue samples from the tumor tissue region at a ratio of 1:3 (i.e. the pathologists will examine the samples from each patient histopathologically), which translates to a tumor tissue prevalence of 75% in the overall tissue samples.

The following calculations were performed using PASS 15 Power Analysis and Sample Size Software (2015). NCSS, LLC. Kaysville, Utah, USA, ncss.com/software/pass and using the methods for calculating sample size for co-primary endpoints of sensitivity and specificity.⁴¹⁻⁴³

Assuming a prevalence of 75% and a sample sensitivity of 85%, the sample size needed to estimate a two-sided 95% sensitivity confidence interval with a width of at most 35% (\pm 17.5% precision assuming asymptotic with continuity correction method) is at least 23.We will use a sample size of 23 in this study.

If the prevalence is as low as 50% in our sample then the width of our 75% sensitivity confidence interval will increase to 40.6% (± 20.3 precision) which still gives a lower bound for the CI above 50%.

The sample size calculation is performed conservatively assuming only 1 measure per patient, but there will be typically 4 per patient which will improve precision of estimates.

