8.3 Data Analyses Plans

The characteristics of participants and information collected before 5-ALA is administered will be summarized using standard statistics, such as mean, SD, median, 1st and 3rd quartiles for continuous variables, and count, percentage for categorical variables.

Analysis of the primary endpoint

To assess the feasibility of using 5-ALA as an adjunct diagnostic imaging tool to detect malignant tumor tissue, the point estimate of sensitivity will be computed according to the following definition:

Sensitivity: proportion of tumor tissues that tested positive on 5-ALA induced fluorescence.

The definition of a positive test is the fluorescence score equal to or greater than 1 while a negative test is considered a score of 0. For the assessment of sensitivity and

specificity, histological diagnoses of any upper aerodigestive head and neck cancer in addition to squamous cell carcinoma, carcinoma in situ, and severe and moderate dysplasia were classified as malignant, whereas light dysplasia and normal tissue will be classified as benign by pathologists. The analysis population includes all patients who sign the inform consent regardless of taking 5-ALA or not. Each patient is expected to contribute multiple samples and the pathologists will determine presence of malignancy in each sample. A contiguous table (fluorescence scores vs. pathological results) that presents the frequency and percentage of each cell will be prepared. A generalized estimating equation (GEE) model accounting for repeated measure within each patient will be used to estimate the sensitivity and specificity.⁴⁴⁻⁴⁵ For sensitivity and specificity, the dependent variable is the PPIX fluorescence test result (positive vs. negative) and the independent variable is presence of tumor cells (tumor vs. normal).

Analysis of the secondary endpoints

To further determine the diagnostic performance of 5-ALA for detecting of malignant tumor tissue, specificity, PPV and NPV will be computed. Specificity will be computed according to the following definition:

Specificity: proportion of normal tissues that tested negative on 5-ALA induced fluorescence.

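### Section 8.2 applies a share of tissue samples to a count of patients, so its 35% and 40.6% interval widths for sensitivity are wider than the planned design implies

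*Combined protocol and SAP*

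**What the plan says.** Section 8.2 describes the sampling first: "Thus each patient is expected to contribute 1 tissue sample from a normal margin region and 3 tissue samples from the tumor tissue region". It reads this ratio as one "which translates to a tumor tissue prevalence of 75% in the overall tissue samples". The calculation follows: "Assuming a prevalence of 75% and a sample sensitivity of 85%, the sample size needed to estimate a two-sided 95% sensitivity confidence interval". The target is a width no greater than 35%, the answer is a minimum of 23, and the margin is given as ±17.5% on this basis: "precision assuming asymptotic with continuity correction method". The 23 is a number of patients (section 8.1). A second scenario puts prevalence at 50% and reports a width of 40.6% (±20.3), with a lower limit still above 50%.

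The section adds that the calculation conservatively takes one reading from each patient, and then says: "but there will be typically 4 per patient which will improve precision of estimates". It does not give the improved precision, the number of tumor readings or a within-patient correlation. The Study Summary repeats the 35% calculation and the remark about conservatism, but not the 50% scenario.

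Section 8.3 plans the analysis on all samples: "A generalized estimating equation (GEE) model accounting for repeated measure within each patient will be used to estimate the sensitivity and specificity".

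**The concern.** Dividing by prevalence suits a study in which each subject is either diseased or not, so that only a fraction of subjects informs sensitivity. Here the 75% arises inside each patient. Every patient is expected to give tumor tissue and normal tissue, so no patient is used up as a normal reading.

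Sensitivity is the primary endpoint (section 2.3) and sections 8.2 and 8.3 set no success threshold. The interval width is therefore the only quantitative basis for 23. If it is computed for a different sampling scheme, the plan does not say how precise its primary result is expected to be under the analysis in section 8.3.

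**Working it through.** **Inputs.** From section 8.2: sensitivity p = 0.85, two-sided 95% interval, asymptotic method with continuity correction, prevalence 0.75 or 0.50, and 3 tumor samples plus 1 normal sample per patient. From section 8.1: 23 patients. The within-patient correlation of tumor readings (ICC) is not in the documents, so a range is shown.

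**Formula.** Half-width h = 1.96 × √(p(1−p)/n) + 1/(2n), with n the number of tumor readings. Cut width = min(1, p + h) − (p − h). Uncut width = 2h.

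**Step 1: reproduce the plan's figures.**

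- n = 17: h = 1.96 × √(0.1275/17) + 1/34 = 0.1697 + 0.0294 = 0.199. The interval is 65.1% to 100% (cut), width 34.9%.
- n = 16: cut width 35.6%, so 17 is the smallest n that meets 35%. Then 17/0.75 = 22.7, which rounds up to **23**.
- 50% scenario: 23 × 0.5 = 11.5, taken as 11. h = 0.2110 + 0.0455 = 0.2565. The interval is 59.4% to 100% (cut), width 40.65%, which matches **40.6%** and a lower limit above 50%. n = 12 gives 39.4%, so 11 was used.

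The 50% scenario mentions a 75% sensitivity interval. At p = 0.75 and n = 11 the lower limit would be 44.9%, which contradicts the stated lower limit above 50%. The figures therefore belong to p = 0.85.

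**Step 2: the ± figures.** The stated widths appear only with the upper limit cut at 100%. The ±17.5% and ±20.3 are half of a cut, asymmetric interval. The distances from 85% down to the lower limits are 19.9 and 25.6 points. Uncut, the widths are 39.8% (n = 17) and 51.3% (n = 11).

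**Step 3: the design as described.** With m tumor samples from each of 23 patients, effective n = 23m / (1 + (m − 1) × ICC).

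| ICC | 3 tumor samples: effective n | Width | 2 tumor samples: effective n | Width |
|---|---|---|---|---|
| 0 | 69.0 | 18.3% | 46.0 | 22.8% |
| 0.3 | 43.1 | 23.6% | 35.4 | 26.4% |
| 0.5 | 34.5 | 26.7% | 30.7 | 28.5% |
| 1 | 23.0 | 31.8% cut, 33.5% uncut | 23.0 | 31.8% cut, 33.5% uncut |

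The cut matters only in the last row. Two tumor samples of four is the within-patient form of 50% prevalence, so the right-hand columns are the counterpart of the plan's 40.6%.

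As a check on the planned analysis, robust logit GEE intervals were simulated (20,000 beta-binomial trials of 23 patients with 3 tumor samples each). Median widths were 16%, 21%, 24% and 29% at these four ICC values, slightly narrower than the formula.

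**The case against.** The strongest reply is that the plan already discloses this. It says the calculation takes one measure per patient, calls that conservative, and says that about four per patient will do better. If that one measure is a sample drawn from a pool that is 75% tumor, 23 readings yield about 17 tumor readings (23 × 0.75 = 17.25) and the result follows. The arithmetic is then sound and the model merely crude. The direction is safe, and the planned design meets 35% at every ICC shown.

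Much of this stands: the computation reproduces, the direction is disclosed, and the choice of 23 is unaffected. What the disclosure does not cover is the unit. The worst case for repeated samples is complete agreement within a patient, and that still leaves one tumor reading from each of 23 patients. Reaching 17 requires six patients with no tumor reading, and reaching 11 requires twelve.

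A reader might infer several stronger things that the documents do not support:

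- **That 17 patients would suffice.** This holds only with the cut at 100%, which the plan does not state. At n = 17 the half-width is 19.9 points, not 17.5. Uncut, 22 readings are needed for a 35% width.
- **That 23 is too few**, because 22/0.75 = 29.3 would call for 30. Dividing by 0.75 does not apply here, and 23 tumor readings give ±16.8 points uncut.
- **That the loss of precision in the 50% scenario cannot occur.** Section 8.2 speaks only of what is typical and expected. Section 8.3 leaves malignancy of each sample to the pathologist and keeps consented patients who never take 5-ALA. Fewer than 23 contributing patients is possible, though a fall to 11 is unlikely.
- **That 32% is a ceiling.** It is a planning value at 85% sensitivity. At 75%, the low end of the range cited in section 8.2, 23 effective readings give a width of 39.7%.

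**Conclusion.** The point holds as a misstatement of expected precision for the primary endpoint. It does not show that the sample size is wrong. The 35% and 40.6% widths describe 17 and 11 tumor readings. For the sampling in section 8.2 the same formula gives about 18% to 32% with three tumor samples per patient and about 23% to 32% with two, over ICC 0 to 1 (33.5% at ICC 1 if uncut). The stated widths are therefore too wide, the error is conservative, and 23 patients meets the 35% target across that range. The ± figures are separately wrong as margins, and they understate the distance to the lower limit.

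This rests on all 23 patients contributing tumor tissue, a sensitivity of 85%, and an assumed ICC. It is worth correcting, but it threatens neither the validity of the trial nor the safety of its patients.

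**What to change.** Keep 23 patients. In section 8.2 and the Study Summary, remove the prevalence factor from the patient count and state the expected precision with its assumptions, for example:

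> If all 23 patients contribute 3 tumor samples and sensitivity is 85%, the expected 95% CI width (asymptotic with continuity correction) is about 18% at ICC 0, 24% at ICC 0.3, 27% at ICC 0.5 and 32% at ICC 1 (upper limit cut at 100%; 33.5% uncut). With 2 tumor samples per patient it is about 23%, 26%, 28.5% and 32%. These are planning values. The ICC is assumed, and precision will be lower if fewer patients contribute tumor tissue or sensitivity is lower.

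In section 8.2, let the two-sample figures replace the 40.6% sentence. In both places, replace the claim that at least 23 are needed with a statement that 23 meets the 35% width across this ICC range, and either delete the ± figures or give the lower limits instead. Do not add that 17 patients would be enough, and do not present 32% as a maximum.

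The cost is a few sentences in two places, with no change to enrolment, procedures or the analysis in section 8.3.

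### Section 8.2 halves intervals that were cut at 100% and prints them as ±17.5% and ±20.3; its 75% label does not fit the 40.6% width; N=23 stands on the cut-width criterion

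*Combined protocol and SAP*

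**What the plan says.** The sample size rests on interval precision for sensitivity, the primary endpoint (section 2.3.1). Section 8.2 begins "Assuming a prevalence of 75% and a sample sensitivity of 85" percent and asks for a "two-sided 95% sensitivity confidence interval with a width of at most 35" percent. In parentheses it restates this target as ± "17.5% precision assuming asymptotic with continuity correction method". The smallest sufficient number is given as 23, and the plan adopts it: "We will use a sample size of 23 in this study". The Statistical Methodology entry of the study summary repeats the base case, including the ±17.5%.

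Section 8.2 then considers 50% prevalence and says that "the width of our 75% sensitivity confidence interval will increase to 40.6% (± 20.3 precision"), "which still gives a lower bound for the CI above 50" percent. The basis is one sample per patient: "The sample size calculation is performed conservatively assuming only 1 measure per patient". Neither place says that the upper limit is cut at 100%.

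**The concern.** A ± figure is a distance from the estimate. With an assumed sensitivity of 85%, ±17.5 points runs to 102.5% and ±20.3 points to 105.3%, both impossible for a proportion. The ± figures therefore cannot describe the interval that produced N. The 75% attached to the second interval is also puzzling, because section 8.2 elsewhere works with 95% confidence and 85% sensitivity.

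Precision is the only reason given for 23 patients, since section 8.2 has no hypothesis test or power calculation. If the ± figures are wrong, a reader gets too favorable an idea of the lower limit, which is the side of interest for a sensitivity estimate. If the 75% is ambiguous, it is unclear which assumption supports the claim that the lower bound exceeds 50%.

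**Working it through.** **Inputs, all from section 8.2:** two-sided 95% confidence (z = 1.96); sensitivity p = 0.85; prevalence 0.75 or 0.50; N = 23; one sample per patient; asymptotic interval with continuity correction. Tumor samples: 23 × 0.75 = 17.25, taken as 17; 23 × 0.50 = 11.5, taken as 11.

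**Formula.** Half-width h = z·√(p(1−p)/n) + 1/(2n), limits p ± h, with n the number of tumor samples.

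**Reproducing the plan's N and widths**

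| Prevalence | n | h (points) | Limits before cut | Full width | Width cut at 100% | Half of cut width |
|---|---|---|---|---|---|---|
| 75% | 17 | 16.97 + 2.94 = 19.9 | 65.1% to 104.9% | 39.8 | 34.9 | 17.5 |
| 50% | 11 | 21.10 + 4.55 = 25.6 | 59.4% to 110.6% | 51.3 | 40.6 | 20.3 |

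- With n = 16 the cut width is 35.6, above 35. The minimum is therefore n = 17, and 17/0.75 = 22.7 rounds up to N = 23, as stated.
- With n = 12 the cut width at 50% prevalence is 39.4, so 11 is the count behind the printed 40.6.
- Without the cut, a width of at most 35 needs n = 22, and 22/0.75 = 29.3 gives N = 30.
- Other methods do not give both figures. The uncorrected asymptotic interval gives N = 22, with 42.2 (n = 11) or 40.4 (n = 12) at 50% prevalence. The uncorrected Wilson interval gives 40.6 at n = 11, but N = 22, and it is not the method named. Corrected Wilson and Clopper-Pearson each give N = 27.

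Of the methods tried, only the stated one with the upper limit cut at 100% gives both N = 23 and 40.6%.

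**The ± figures.** Both printed values equal the last column of the table. Taken literally:

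- 85 ± 17.5 = 67.5% to 102.5%. The actual lower limit is 65.1%, a difference of 67.5 − 65.1 = 2.4 points.
- 85 ± 20.3 = 64.7% to 105.3%. The actual lower limit is 59.4%, a difference of 64.7 − 59.4 = 5.3 points.

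The cut intervals are asymmetric: −19.9/+15.0 and −25.6/+15.0 around 85%.

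**The 75% label, at n = 11**

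| Confidence | Sensitivity | Lower limit | Width (cut at 100%) |
|---|---|---|---|
| 75% | 85% | 68.1% | 31.9 |
| 95% | 75% | 44.9% | 55.1 |
| 75% | 75% | 55.4% | 39.1 |
| 95% | 85% | 59.4% | 40.6 |

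Only the last row gives the printed width. The statement that the lower bound exceeds 50% is true there, and false at 75% sensitivity with 95% confidence.

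**Effect of several samples per patient.** The documents give no within-patient correlation (ICC), so a range is assumed. With 3 evaluable tumor samples from each of 23 patients, the effective n is 69/(1 + 2·ICC), which is 69, 34.5 and 23 at ICC 0, 0.5 and 1. The corrected half-widths at 85% are 9.1, 13.4 and 16.8 points.

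**The case against.** The strongest reply is that little turns on this. The operative criterion is a total width "with a width of at most 35" percent, which is met, and the ± is a parenthetical halving of it. The trial is a single-arm pilot without a success threshold for sensitivity, and the analysis uses a GEE model on all samples (section 8.3), not this planning interval. With three tumor samples per patient the half-width stays inside ±17.5 even at ICC 1. At 50% prevalence, if each patient gave two tumor samples, the effective n at ICC 1 would be 46/2 = 23 and the half-width 16.8 points, inside ±20.3. All of this stands. It limits the consequence, but it does not make the printed figures right for the one-sample basis on which the plan declares them.

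A second reply is that 75% may be a slip for 95%, or a clumsy reference to the 75%-prevalence base case from which the width increases. A slip for 95% is plausible and agrees with the numbers. The prevalence reading does not repair the sentence, because the interval that it describes is the one at 50% prevalence. Section 8.2 also cites 75% as the low end of the sensitivities reported in glioma, so a reader could well take it as a sensitivity.

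A third reply is that the cut at 100% is inferred, so N=23 is confirmed only conditionally. That is correct. If ±17.5 points on each side had been the aim, the stated method would need 22 tumor samples and N=30.

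**Conclusion.** The concern holds. Both ± figures are half of a one-sidedly cut interval and understate the distance from 85% to the lower limit: 17.5 printed against 19.9 points, and 20.3 against 25.6. The 75% label conflicts with the 40.6% width beside it; that width belongs to 95% confidence at 85% sensitivity. N=23 and the widths of 34.9% and 40.6% are right for the cut interval on one sample per patient. These conclusions assume tumor counts rounded down to 17 and 11 and a cut at 100% that the plan does not state; the match to N and both widths supports these assumptions. The plan's claim that one sample per patient is conservative also holds in the three-tumor-sample case above. The error affects the reported justification, not a test, a decision threshold or enrolment.

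**What to change.** In section 8.2 and the study summary, delete ±17.5% and give the interval at 75% prevalence as 65% to 100%, stating that the upper limit is truncated at 100%. In section 8.2, delete ±20.3 and give the interval at 50% prevalence as 59% to 100%, with the same statement. Replace the 75% label by a 95% confidence interval at 85% sensitivity; if another assumption was meant, recompute the width and the lower bound for it. Say that N=23 meets the criterion of total width after truncation. If a distance of 17.5 points on each side was the real target, N must be reconsidered.

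Optionally, add the precision expected from three tumor samples per patient, about ±9 to ±17 points over ICC 0 to 1, labeled as an assumption.

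The cost is two reworded sentences in section 8.2 and one in the study summary. On the width criterion, N, the analysis and enrolment do not change.

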8.3 Data Analyses Plans

The characteristics of participants and information collected before 5-ALA is administered will be summarized using standard statistics, such as mean, SD, median, 1st and 3rd quartiles for continuous variables, and count, percentage for categorical variables.

Analysis of the primary endpoint

To assess the feasibility of using 5-ALA as an adjunct diagnostic imaging tool to detect malignant tumor tissue, the point estimate of sensitivity will be computed according to the following definition:

Sensitivity: proportion of tumor tissues that tested positive on 5-ALA induced fluorescence.

The definition of a positive test is the fluorescence score equal to or greater than 1 while a negative test is considered a score of 0. For the assessment of sensitivity and

specificity, histological diagnoses of any upper aerodigestive head and neck cancer in addition to squamous cell carcinoma, carcinoma in situ, and severe and moderate dysplasia were classified as malignant, whereas light dysplasia and normal tissue will be classified as benign by pathologists. The analysis population includes all patients who sign the inform consent regardless of taking 5-ALA or not. Each patient is expected to contribute multiple samples and the pathologists will determine presence of malignancy in each sample. A contiguous table (fluorescence scores vs. pathological results) that presents the frequency and percentage of each cell will be prepared. A generalized estimating equation (GEE) model accounting for repeated measure within each patient will be used to estimate the sensitivity and specificity.⁴⁴⁻⁴⁵ For sensitivity and specificity, the dependent variable is the PPIX fluorescence test result (positive vs. negative) and the independent variable is presence of tumor cells (tumor vs. normal).

Analysis of the secondary endpoints

To further determine the diagnostic performance of 5-ALA for detecting of malignant tumor tissue, specificity, PPV and NPV will be computed. Specificity will be computed according to the following definition:

Specificity: proportion of normal tissues that tested negative on 5-ALA induced fluorescence.

The definition of a positive test is the fluorescence score equal to or greater than 1 while a negative test is considered a score of 0. For the assessment of sensitivity and specificity, histological diagnoses of any upper aerodigestive head and neck cancer in addition to squamous cell carcinoma, carcinoma in situ, and severe and moderate dysplasia were classified as malignant, whereas light dysplasia and normal tissue will be classified as benign by pathologists. The analysis population includes all patients who sign the inform consent regardless of taking 5-ALA or not. Each patient is expected to contribute multiple samples and the pathologists will determine presence of malignancy in each sample. A contiguous table (fluorescence scores vs. pathological results) that presents the frequency and percentage of each cell will be prepared. A generalized estimating equation (GEE) model accounting for repeated measure within each patient will be used to estimate the sensitivity and specificity. For sensitivity and specificity, the dependent variable is the PPIX fluorescence test result (positive vs. negative) and the independent variable is presence of tumor cells (tumor vs. normal).

For PPV and NPV, a generalized estimating equation (GEE) model accounting for repeated measure within each patient will be used. The dependent variable is presence of tumor, and the independent variable is the test result. The point estimate along with a corresponding two-sided 95% confidence interval will be provided using PROC GENMOD.

The 5-ALA related adverse events will be recorded using standardized toxicity criteria and known side effect profile. Frequency of each observed adverse event will be calculated at each monitor time point. The rate of each adverse effect will be estimated as the number of adverse events within 6 weeks after surgery divided by the number of person days followed. The point estimate of the incidence rate along with a corresponding two-sided 95% confidence interval will be provided using PROC GENMOD. 46

The analyses will be conducted using SAS 9.4 software. Copyright ©[2002-2012] SAS Institute Inc.

